## 1. Study aim, background, and design

Coronavirus SARS-CoV-2, causing COVID-19, has infected over 20 million people and killed over 700,000 as of August 2020. Although, the vaccination campaign is ramping up, vaccination hesitancy in the United States represents up to 25-30% of the population (1), and hospitalizations and deaths are still at the level of 2020. Apart from corticosteroids (2), most available therapeutic options are at best marginally efficient in reducing disease severity and mortality and extremely expensive (3-5). Therefore, the systematic investigation of clinically approved drugs is a priority in order to determine what does improve the disease and invest resources to go to full-scale production. Our current understanding of the disease is that COVID-19 deaths result from an inappropriate immune response with outpouring of pro-inflammatory chemokines leading to lung infiltration and hyperactivation of monocytes and macrophages producing pro-inflammatory cytokines (cytokine storm), resulting in lung edema, reduced gas exchange, and ultimately leading to acute respiratory distress syndrome and multiorgan failure (1-8). *Men with COVID-19 have a uniformly more severe outcome than women.* In series from China, Europe and the U.S., COVID-19 mortality was consistently 1.5 to 2-fold higher in men than in women, suggesting that female biological sex is protecting women from COVID-19 mortality (9-13). It is established that women exhibit heightened immune responses to viral infections compared to men (14), which is at least partially due to the genetic benefit of gene dosage in X-linked immune-response genes. Ovarian steroids, however, also play a protective role. In New York City, among 5700 hospitalized patients, the female protection from COVID-19 mortality was observed at all ages, but was more pronounced in subjects under 50 years of age (18% mortality in women) compared to patients > 50 years of age (40.5% mortality in women) (13), suggesting that ovarian steroids are involved in mitigating COVID-19 mortality in pre-menopausal women. Further, the analysis of electronic health records of over 68,000 COVID-19 patients revealed that estrogen therapy is associated with more than 50% reduction in mortality (15). The main female steroids, 17 $\beta$ -estradiol and progesterone exhibit potent immuno-modulatory and anti-inflammatory actions via estrogen and progesterone receptors expressed in all immune cells, including epithelial cells, macrophages, dendritic cells, CD4+ and CD8+ lymphocytes, and B cells (14,16). Progesterone also acts partially via the glucocorticoid receptor. Together estradiol and progesterone produce a state of *decreased innate immune cells production of proinflammatory cytokines, enhanced T cells anti-inflammatory responses and immune tolerance, and enhanced B-cell-mediated antibody production* (14,17,18). The National Institutes of Health (NIH) COVID-19 Treatment Guidelines Panel recommends the use of dexamethasone 6 mg per day for up to 10 days or until hospital Discharge (whichever comes first) as standard of care (SOC) for the treatment of hospitalized COVID-19 patients who require supplemental oxygen but who are not mechanically ventilated and for the treatment of hospitalized patients who are mechanically ventilated. Remdesivir is SOC at Tulane for COVID-19 patients who require supplemental oxygen but who are not mechanically ventilated. We believe that in hospitalized COVID-19 patients, a short treatment with the combination estradiol and progesterone, administered early and as a prevention in addition to SOC, will prevent or mitigate the cytokine storm while increasing antibody production and prevent severe outcomes, without side effects (18). Therefore, it will provide steroid immunomodulation without immunosuppression. The advantage of repurposing estradiol and progesterone compounds is the depth of knowledge regarding their clinical efficacy and toxicity that has accumulated from decades of clinical and basic studies. Estradiol and progesterone are widely available in hospitals, inexpensive, manufacturable to scale, and can be prescribed immediately. Please note there is no increased risk of blood clot following acute and systemic administration of natural hormones. The risk exists following chronic and orally administered synthetic hormones (as discussed below).

## **Study Objectives**

The purpose of this study is to determine to what extent a short and preventive systemic steroid therapy with estradiol and progesterone, administered early to hospitalized and confirmed COVID-19 positive patients of both sexes in addition to standard of care (SOC) can reduce the severity of symptoms and outcomes compared to SOC alone. Note that premenopausal women will be included as acute illness can alter the function of the hypothalamo-pituitary gonadal axis, creating a functional hypogonadism leading to low estrogen levels.

This study has two study arms. One arm will receive standard of care (SOC) with administration of placebo-equivalent with similar frequency, volume and method of administration as for the drug below. The other arm will receive SOC along with the study drugs, a single IM injection of long-acting estradiol cypionate (Depo-Estradiol) 5mg upon admission and a daily oral administration of progesterone 200mg (Progesterone generic 200mg) for 5 days. Clinical status will be assessed at day 14 and day 28 and 60 days.

## **Study Design**

Study Type:	Interventional (Clinical Trial)
Estimated Enrollment:	120 participants
Allocation:	Randomized, placebo-equivalent controlled
Masking:	Double-blinded
Primary Purpose:	Treatment
Setting:	Inpatient hospitalization

## **2. Subject population**

Up to 120 participants hospitalized in the Department of General Internal Medicine and Geriatrics at the Medical Center with mild to severe COVID-19 (WHO ordinal scale score 3-5, Fig.2) confirmed by SARS-CoV-2 PCR test will be recruited for this study. Participants will be recruited at admission by the medical staff of the Department of General Internal Medicine and Geriatrics under the leadership of [name] (Co-I) who will identify participants that meet study eligibility criteria from their admission list.

### **2.1. Sample Size Considerations**

Sample size calculations are based on 80% Power, using a two-sided Pearson's Chi-square Test for Proportion Differences at the 5% significance level. It is estimated that between 60% and 70% of hospitalized patients with mild or severe disease will improve clinically and become ambulatory after standard treatment (WHO ordinal scale score 1-2 Fig.2)). Table 1 presents the sample sizes that are required in each treatment group to detect a significant difference in the percent of hospitalized patient leading to an ambulatory disease (shift from category 5-8 to category1-2 in 20%, 25%, 30% or 35% of hospitalized patients after treatment with estradiol (E2) and progesterone (P4)). Efforts will be made to recruit 60 patients in each treatment group in order to stratify by disease severity, age and gender.

Table 1.		
Treatment	Percent leading to a scale 1-2	Sample Size
SOC	60%	32
SOC + E2 + P4	90%	32
SOC	60%	22
SOC + E2 + P4	95%	22
SOC	70%	62
SOC + E2 + P4	90%	62
SOC	70%	36
SOC + E2 + P4	95%	36

An interim analysis will be performed at 50% enrollment to determine to what extent a strong treatment efficacy warrants stopping the trial early. Table 2 presents interim sample sizes and required Z test statistics for comparing two proportions at each of stage of a O'Brien-Fleming alpha-spending sequential design (24). Based on 80% power and an overall 5% significance level, if the interim analysis for the first 60 enrolled patients results in differences that are more than 2.96 standard deviations from 0, the trial will end, and treatment efficacy will be concluded. Otherwise, the trial will enroll the total 120 patients.

Table 2.			
	Treatment	Sample Size	Standardized Z test Statistic
Stage 1	SOC	30	2.96
	SOC + E2 + P4	30	
Stage 2	SOC	60	1.96
	SOC + E2 + P4	60	

## 2.2 Inclusion Criteria:

1. Hospitalization at the Medical Center in the Department of General Internal Medicine and Geriatrics with COVID-19 (WHO Ordinal scale score 3-5, Fig.2) and confirmed by SARS-CoV-2 PCR.
2. Respiratory symptoms (fever, shortness of breath or cough) or abnormal lung exam or chest imaging characteristic of mild to severe COVID-19 pneumonia\*.
3. Patient and/or legally authorized representative (LAR) agrees to comply with study procedures and the collection of blood samples per protocol
4. Patient and/or LAR agrees to be placed on prophylactic dose of anticoagulation for prevention of deep venous thrombosis (DVT) (if necessary).

5. Patient or legally authorized representative has signed informed consent
6. Women of childbearing age with a negative pregnancy test on admission

\*Severity of COVID-19 defined by FDA guidance document “COVID-19: Developing Drugs and Biological Products for Treatment or Prevention Guidance for Industry” (<https://www.fda.gov/media/137926/download>).

## **2.3 Exclusion Criteria:**

1. Patient under 18 years of age
2. Critical COVID-19 (respiratory failure requiring intubation and mechanical ventilation, shock, multi-organ failure)
3. Pregnant women confirmed by pregnancy test
4. Women who are within six weeks of postpartum
5. Patient is not hospitalized at the Medical Center with confirmed COVID-19
6. Patient included in another COVID-19 trial (excluding hydroxychloroquine and dexamethasone)
7. Women already treated by estrogen and or progestogen therapy two weeks prior to admission
8. Men already treated by testosterone therapy prior to admission
9. History of breast or endometrial cancer
10. Abnormal genital bleeding
11. Active or recent (e.g., within the past year) stroke or myocardial infarction
12. History of blood clots including deep vein thrombosis related to clotting disease, or pulmonary emboli (prior to hospitalization).
13. History of liver dysfunction or disease.
- 14. Patients with end-stage renal disease**
15. Patients taking inhibitors of CYP3A4 such as erythromycin, clarithromycin, ketoconazole, itraconazole, and ritonavir.
16. Patients taking St. John’s Wort preparations (*Hypericum perforatum*), phenobarbital, carbamazepine, and rifampin.
17. Patients within 6 weeks of major orthopedic surgery

## **3. Procedure**

The study will begin after the study team obtains IND from the FDA and IRB approval from Tulane University Biomedical IRB. The study will utilize the Medical Center Research Pharmacy for randomization, the accountability, storage, dispensing, handling, and disposal of drugs. The Clinical Translational Unit (CTU) will also participate in the implementation of the study. We estimate that the study will be complete within 12 months.

### **3.1 Collection of blood samples**

The collection of routine blood samples and patient monitoring will be conducted as part of the standard of care procedures that are utilized at the hospital for COVID-19 patients. The collection of blood samples (CBC with differential, blood chemistry, inflammation markers) is to monitor disease severity and is independent from this protocol, but we will use the data in our analysis as explained in section 3.5. Women of childbearing age will have a pregnancy test on admission

An additional blood sample will be collected for our study at admission and after 5 days of treatment. We will collect about 1-5 teaspoons of blood at these two time points. This blood sample will be stored in [name] lab for 1) isolation of peripheral blood mononuclear cells (PBMC) to assess the effect of treatment on immune cells populations by flow cytometry and PBMC gene expression by RNA-Seq 2) and metabolomics profiling to determine metabolic and molecular signatures of the efficacy of treatment. De-identified serum and PBMC frozen samples will be transferred to the University of Michigan Metabolomics Core to perform untargeted metabolomic analyses. University of Michigan will not receive identifiable information nor a link to identifiers related to the samples.

Additionally, we propose to use the serum and PBMC from our collected blood samples to perform multi-dimensional analysis in the Center for Translational Research in Infection and Inflammation (Collaboration with [name]), and the laboratories of [name] and [name] at Tulane University School of Medicine. Blood samples will be stored for up to 3 years.

### **3.2 Treatment arms and interventions**

**Treatment Arm:** Standard of Care\* along with Estradiol Cypionate 5mg intramuscular injection at admission and Progesterone 200mg by mouth daily for 5 days starting at admission.

**Control Arm:** Standard of Care along with placebo-equivalent injection of normal saline at admission and placebo-equivalent pill folic acid 400 mg pill daily for 5 days starting at admission. The dose of folic acid (400 mg daily for 5 days) is safe. Participants will be able to take additional folic acid (e.g., over the counter vitamins, or through food) should they choose, as there is no safety concern for overdose over 5 day period of folic acid. Folic acid is not expected to have a treatment or preventive effect for SARS-CoV-19 and is considered a placebo-equivalent product for this study.

\*Standard of Care at the Medical Center is consistent with the National Institutes of Health (NIH) COVID-19 Treatment Guidelines Panel and consists of *dexamethasone 6 mg per day* for up to 10 days or until hospital Discharge (whichever comes first) for the treatment of hospitalized COVID-19 patients who require supplemental oxygen but who are not mechanically ventilated and in hospitalized patients who are mechanically ventilated. Remdesivir is SOC at Tulane for COVID-19 patients who require supplemental oxygen but who are not mechanically ventilated.

#### **Blinding:**

This is a blinded study. However, the medications are not identical-appearing. The dosing is also different for the oral study drug and placebo (folic acid) so blinding will operate in different ways across those involved in the study to preserve blinding for the participants, those who directly interact with them, and measurement of the study endpoints:

- Participants will be blinded. The injection syringe for Estradiol Cypionate or normal saline will be covered with blinding tape to mask the difference in color. The bottles of oral medications will not identify the treatment allocation. Medication bottles will be labeled to say “Progesterone 200mg or folic acid 400 mg).
- Treating clinicians and study team will be blinded
- Study pharmacy staff will be unblinded, as they will prepare and blind the study medications.

### **Dosing Instructions:**

Estradiol cypionate 5 mg (1mL) or normal saline (1 mL) will be administered intramuscularly. One pill of oral progesterone 200 mg or Folic acid 400 mg will be administered orally at bedtime with a glass of water.

### Hazardous Drugs Handling Considerations

Estradiol Cypionate and progesterone are hazardous agents (NIOSH 2016 [group 2]). NIOSH recommends single gloving for administration of intact tablets or capsules. For IM preparation, NIOSH recommends double gloving, a protective gown, and ventilated engineering controls (a class II biological safety cabinet or a compounding aseptic containment isolator). Double gloving and a gown are required during IM administration.

### **3.3 Outcome Measures**

For all randomized patients according to section 2.2, demographic and clinical variables, including sex, age, race/ethnicity, BMI, symptoms, vital signs (blood pressure, respiratory rate, temperature, oxygen saturation), chronic comorbidities through diagnosis codes, medications, clinical course during hospitalization (described in primary outcome below) will be reviewed in the patients' medical charts. Laboratory measurements including when available CBC, blood chemistry, liver function test, creatinine, BUN, lactate, troponin, ferritin, CRP, procalcitonin, Brain-type natriuretic peptide, D-dimer, interleukin-6, G6PD. We will review the participants' medical records for up to 6 months after hospital discharge.

#### **Primary outcome:**

For all randomized patients with baseline inclusion criteria, WHO ordinal scale score 3-5, the primary efficacy end point will be the proportion of patients who achieve scores 1 or 2 on the 9-point World Health Organization (WHO) ordinal scale (Fig. 2) through day 28.

#### **Secondary outcomes:**

For all randomized patients, the following secondary end points will be assessed at day 14, 28 and 60

1. Length of hospital stay
2. Duration of mechanical ventilation
3. Cause of death and number of days death occurred after admission
4. Readmission
5. Change in biological markers below between admission and occurrence of primary endpoint (2 values at least 2 days apart)
6. Grade 3 and 4 adverse events
  
7. Serious adverse events

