No member of the DSMB will have direct involvement in the conduct of the study. The DSMB will review and evaluate the accumulated study data for participant safety, adverse events, study conduct, progress, adherence to the protocol and efficacy. The DSMB will consider study-specific data as well as relevant background knowledge about COVID-19, estrogen and progesterone therapy, and the patient population under study. The data will remain blinded. The frequency of DSMB meetings will depend on the rate of enrollment but will roughly occur quarterly. The DSMB meetings will be private and closed meetings. [name] will be responsible for convening meetings by conference calls or Zoom videoconferences or as face-to-face meetings, and coordinating the distribution of meeting materials to DSMB members. The written open session reports from DSMB meetings will be submitted to the Tulane IRB.

We will implement a group sequential trial framework with the option for stopping for safety or harm with an early interim look once 30 patients finish the Day 28 assessment. This will allow the DSMB to evaluate trial safety data. A decision about study continuation will be made based on the independent DSMB recommendations. The DSMB will convene if study participants experience a higher rate than the background rate of thromboembolic disease. The DSMB will also convene when  $\geq$  Grade 3 AE are observed and considered related to drug or not.

We will follow-up in person or by telephone for all subjects in your trial for any adverse events/serious adverse events (AEs/SAEs) and mortality at Day 60.

Adverse events will be graded according to Common Terminology Criteria for Adverse Events (CTCAE) Version5 and taken care with the corresponding specialized clinical management of the SAE.

Grade 1 adverse events (asymptomatic or mild symptoms; clinical or diagnostic observations only; intervention not indicated) or Grade 2 adverse events (moderate; minimal, local or noninvasive intervention indicated; limiting age-appropriate instrumental activity of daily living): such as breast tenderness, nausea, vomiting, bloating, stomach cramps, headaches, vaginal itching, abnormal uterine bleeding will not require discontinuation of treatment.

Grade 3 (severe) like DVT and 4 (life-threatening) serious adverse events such as MI, stroke, POME, anaphylaxis will be managed by treatment discontinuation (except SOC) and appropriate specialized clinical management of the SAE.

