### **3.4 Statistical Analysis**

For all randomized patients according to section 2.2, clinical outcomes and demographic characteristics will be summarized and presented separately for the treatment group and the control group, as well as overall for all patients. Categorical variables such as the primary outcome, readmission, as well as race and sex will be summarized with counts and percentages. Quantitative outcomes, such as length of stay, change in biological markers, age and BMI will be summarized with means, medians, standard deviations, and interquartile ranges. Univariate analyses will be performed as the primary method to assess the unadjusted effect of treatment on the primary outcome and on readmission rate using the Pearson Chi-square test. Differences in average length of stay and in change in biological markers will be assessed with either a two-sample t test or the Mann-Whitney nonparametric test. Multivariate analyses will be performed to compare treatment to control responses while adjusting for various co-factors. Multiple logistic regression will be used as supportive method to test for significant differences in the proportion with the primary outcome, between the active treatment and placebo-equivalent groups, while adjusting for age, race, sex, bmi and other potential co-factors. For the secondary outcomes. multiple logistic regression will also be used to test for significant differences in the proportion readmits, between the active treatment and placebo-equivalent groups, and multiple linear regression will be used to test for significant differences in average length of stay and changes in biological markers, between the treatment and SOC groups, while adjusting for potential influencing co-factors.

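### The plan does not say which day's length of stay is compared, or how stays still open on that day or ended by death enter the comparison

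*Combined protocol and SAP*

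**What the plan says.** Section 3.3 introduces its seven secondary outcomes with "For all randomized patients, the following secondary end points will be assessed at day 14, 28 and 60". The first is "Length of hospital stay", with no further definition.

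Section 3.4 says quantitative outcomes, length of stay among them, "will be summarized with means, medians, standard deviations, and interquartile ranges". For the unadjusted comparison, "Differences in average length of stay and in change in biological markers will be assessed with either a two-sample t test or the Mann-Whitney nonparametric", and no rule is given for choosing between the two. For the adjusted comparison, "multiple linear regression will be used to test for significant differences in average length of stay and changes in biological markers".

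Two other statements bear on what data will exist. Section 3.3 says "We will review the participants' medical records for up to 6 months after hospital discharge", and the safety monitoring text provides for follow-up of "adverse events/serious adverse events (AEs/SAEs) and mortality at Day 60". Death is a separate secondary outcome and is not linked to length of stay.

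The documents give no main assessment day for length of stay, no treatment of a stay unfinished on that day, no treatment of a stay ended by death, and no time-to-discharge method.

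**The concern.** A t test, a Mann-Whitney test and a linear regression each need one value per patient. On Day 14 or Day 28 a patient who is still admitted has no completed stay. Take three survivors discharged on Days 13, 20 and 45. On Day 14 the second and third are inpatients. Either each scores 14, almost the same as the first, or each has no value and leaves the comparison. On Day 28 the same happens to the third.

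Capping and dropping give different results, and so do the three days. An analyst could reach several lengths of stay for the same patients, and the plan does not choose among them. If the treatment works, the open stays lie mainly in the control arm, so both expedients understate the saving in days. A stay ended by death raises a second problem: counted at face value, it is a short stay and looks favourable.

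**Working it through.** **Inputs.** Section 2.1 gives the control rate: "It is estimated that between 60% and 70% of hospitalized patients with mild or severe disease will improve clinically and become ambulatory after standard treatment". Table 1 sets treated rates of 90% and 95%, and 60 patients per arm are planned. The documents give no distribution, standard deviation or effect for length of stay, so the distributions and death shares below are assumptions.

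**Table 1 first.** The pooled-variance formula for two proportions (two-sided 5%, 80% power, no continuity correction) gives 31.5, 21.1, 61.6 and 35.1 per arm. Rounded up, these are 32, 22, 62 and 36, exactly as printed. The response rates can therefore be used as design values.

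**Who has not left hospital alive by Day 28.** On the ordinal scale in Figure 2, scores 3-7 are inpatients and 8 is death. Taking score 1-2 by Day 28 as discharged alive, the remainder is 30-40% of controls (18-24 of 60) and 5-10% of treated patients (3-6 of 60). These counts mix patients still admitted with patients who have died.

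**Illustration at 70% v 90%: exponential stays, no deaths.** Let S(t) be the share still admitted, with S(28) = 0.30 and 0.10.
- Mean completed stay = 28 / (-ln S(28)): 28/1.204 = 23.26 and 28/2.303 = 12.16 days. Difference 11.1.
- Mean capped at T = mean × (1 - S(T)). At Day 28: 23.26 × 0.70 = 16.28 and 12.16 × 0.90 = 10.94. Difference 5.3.
- Mean with open stays dropped = (capped mean - T × S(T)) / (1 - S(T)). At Day 28: (16.28 - 8.40)/0.70 = 11.26 and (10.94 - 2.80)/0.90 = 9.05 (unrounded inputs). Difference 2.2.

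| Difference in mean days | Day 14 | Day 28 | Day 60 | Completed |
|---|---|---|---|---|
| 70% v 90%, capped | 2.2 | 5.3 | 9.4 | 11.1 |
| 70% v 90%, dropped | 0.6 | 2.2 | 6.6 | 11.1 |
| 60% v 90%, capped | 2.9 | 7.4 | 14.2 | 18.4 |
| 60% v 90%, dropped | 0.8 | 2.8 | 9.0 | 18.4 |

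At Day 28, capping keeps 48% (70% v 90%) or 40% (60% v 90%) of the completed difference; dropping keeps 20% or 15%.

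**Power** (simulated, 60 per arm, 70% v 90%, same model).

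| | Completed | Day 28 capped | Day 28 dropped | Day 14 capped | Day 14 dropped |
|---|---|---|---|---|---|
| t test | 94% | 87% | 28% | 69% | 10% |
| Mann-Whitney | 86% | 84% | 30% | 74% | 9% |

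**Tail of the distribution** (Weibull, 70% v 90%, no deaths).

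| Shape | Completed | Day 28 capped | Day 28 dropped |
|---|---|---|---|
| 0.8 | 14.0 | 5.6 (40%) | 2.2 (16%) |
| 1.5 | 7.8 | 4.6 (59%) | 2.1 (27%) |
| 2.0 | 6.3 | 4.05 (65%) | 1.9 (31%) |

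Capping at Day 14 still leaves under a fifth of the difference in the two lighter-tailed cases (1.5 of 7.8 and 1.0 of 6.3).

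**Deaths** (lognormal stays, sigma 0.7, 60% v 90%). With no deaths the completed difference is 15.3 days. If 90% of Day 28 non-responders die in hospital between Days 3 and 28 and each death is counted as a short stay, it is 5.1. Capping at Day 28 then changes it only to 4.3. In that case the handling of death matters far more than the cut-off.

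**The case against.** The strongest reply is that nothing in the plan caps or drops a stay. Section 3.4 attaches no day to average length of stay. The line listing three days covers seven outcomes, one of which (marker change) runs to occurrence of the primary endpoint, so it can be read as a follow-up schedule. Day 60 is on the list and the chart review runs for months after discharge, so nearly every stay can be completed: in the exponential model only 4.5-8.4 of 60 controls and 0.1-0.4 of 60 treated patients are still admitted at Day 60. Specifying all randomized patients also argues against dropping anyone. A capped stay is a legitimate restricted mean if declared, and capped Mann-Whitney at Day 28 loses almost no power.

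Much of this stands. A reader might infer that the plan prescribes truncation; it does not, and the defect is its silence. A reader might also take 18 v 6 of 60 as patients still in hospital at Day 28. The documents do not support that, because Table 1's non-responders include deaths, and the background section cites mortality of 18% and 40.5% in hospitalized women by age group.

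The reply does not settle the matter. That completed stays are obtainable does not mean the plan says to use them. The schedule reading is possible but not stated, and no reading says what value a patient who dies in hospital receives.

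**Conclusion.** The concern holds as a gap in definition. The plan names three assessment days and methods that need one value per patient, but not which day is analysed or how open stays and in-hospital deaths enter. A literal Day 14 or Day 28 comparison of average stay would be distorted.

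The size is conditional. If the treatment works as Table 1 assumes, capping at Day 28 keeps roughly 40-65% of the difference in mean days across the no-death exponential and Weibull cases examined, and dropping keeps roughly 15-31%. More deaths reduce the loss from capping but add their own distortion. It would be too strong to say that the plan shrinks the effect: with no treatment effect open stays balance on average, and the severe loss of power at Day 28 comes from dropping patients, not from capping. This is one secondary outcome; the primary endpoint is unaffected. It is worth correcting because the remedy is cheap.

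**What to change.** In section 3.3, define length of stay once, as time to discharge alive over follow-up to Day 60. Patients still admitted are censored at Day 60, and death in hospital is a competing event.

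In section 3.4, for this outcome, replace the t test, Mann-Whitney test and linear regression with cumulative incidence of live discharge by arm, compared by Gray's test. Use a Fine-Gray or cause-specific Cox model, named in advance, for the adjusted analysis. Report Days 14 and 28 as the cumulative proportion discharged alive, read from the same curve.

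The cost is revised wording in the secondary outcome list and in the statistical analysis section. No new data are needed, because discharge dates come from the chart review. The small downside is that the main result becomes a cumulative incidence or hazard ratio instead of a mean difference in days. A mean restricted to 60 days could be added as a supplementary summary, with its treatment of deaths stated.

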#### **5. Benefits**

There is immediate benefit for individual subjects in this study as we expect the hormonal treatment to prevent mortality and to decrease the severity of COVID-19 disease. Additionally, the knowledge gained by this study may provide important insights into the pathogenesis of the disease. Overall this study will benefit society as it will address the question of whether hormones partially explain the female protection from COVID-19 and if we can use hormone therapy for life saving off-label therapeutic applications.

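### No between-arm analysis of all-cause mortality is specified, and the ventilation and length-of-stay endpoints have no rule for death

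*Combined protocol and SAP*

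**What the plan says.** Section 3.3 opens its list of secondary outcomes with "For all randomized patients, the following secondary end points will be assessed at day 14, 28 and 60". Item 1 is "Length of hospital stay", item 2 is "Duration of mechanical ventilation" and item 3 is "Cause of death and number of days death occurred after admission". None says how a patient who dies enters the two durations, or how a survivor enters item 3.

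Section 3.4 describes numerical data under "Quantitative outcomes, such as length of stay, change in biological markers", with means, medians, standard deviations and interquartile ranges. It names these between-arm analyses:

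- primary outcome and readmission: chi-square test and logistic regression;
- length of stay and biomarker change: t test or Mann-Whitney test, and linear regression;
- death and ventilation duration: none named.

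Mortality appears in three other places. Under Safety measures and monitoring, all subjects are followed for "adverse events/serious adverse events (AEs/SAEs) and mortality at Day 60". Section 5 states "we expect the hormonal treatment to prevent mortality". Section 1 cites an association of estrogen therapy with a mortality reduction of more than 50%.

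**The concern.** Days to death can be observed only in patients who die, a group formed after randomisation and open to the effect of treatment. Comparing that number between arms does not compare randomised groups, and it does not show how many died.

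Ventilation has a related problem. Intubated patients are excluded at entry (Section 2.3, criterion 2), so all ventilation begins after randomisation, and death cuts its duration short. Death in hospital shortens length of stay in the same way, and that endpoint is formally tested. In each case an early death yields a small value, which on a duration scale reads as a good result.

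At stake is whether the trial can report its effect on mortality by a method fixed in advance, and whether a shorter stay or shorter ventilation can be read as benefit.

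**Working it through.** **Inputs.** From the documents: 60 per arm, two-sided 5% level, 80% power (Section 2.1). The documents give no expected mortality, ventilation rate or stay for these patients, so every such rate below is an assumption. Halving mortality is used because it is close to the effect cited in Section 1.

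**1. Formula check on the plan's own figure.** With p̄ the mean of the two rates, n per arm = [1.96√(2p̄(1−p̄)) + 0.842√(p1(1−p1) + p2(1−p2))]² / (p1−p2)². For 70% vs 90%: [1.96√0.32 + 0.842√0.30]² / 0.04 = 61.6, so 62. The four scenarios of Table 1 come out at 32, 22, 62 and 36, as printed. The plan gives no such figure for mortality.

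**2. Days to death.** Assume 12 control deaths, 6 on day 4 and 6 on day 20, and 6 treatment deaths.

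- Control mean: (6×4 + 6×20)/12 = 12 days.
- Treatment prevents the late deaths: mean 4 days.
- Treatment prevents the early deaths: mean 20 days.

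Mortality is 12/60 vs 6/60 in both cases, yet the summary moves in opposite directions.

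**3. Ventilation duration.** Assume 12 ventilated per arm, 6 control and 3 treatment deaths, and survivors ventilated for 14 days. If deaths come at ventilation day d, the means are (6d + 6×14)/12 for control and (3d + 9×14)/12 for treatment.

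| d | Control | Treatment |
|---|---|---|
| 5 | 9.5 | 11.75 |
| 10 | 12.0 | 13.0 |
| 14 | 14.0 | 14.0 |
| 18 | 16.0 | 15.0 |

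The arm with half the deaths looks worse when deaths are early, equal at day 14, and better at day 18. Scoring the 48 never-ventilated patients as zero does not cure this: at d = 5 the means are 12×9.5/60 = 1.9 and 12×11.75/60 = 2.35.

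Ventilator-free days to Day 28 with death scored 0 give, among the ventilated, 6×14/12 = 7.0 for control and 9×14/12 = 10.5 for treatment, whatever d is. If the other 48 survive unventilated (28 days each), the means over all 60 are (1344 + 84)/60 = 23.8 and (1344 + 126)/60 = 24.5.

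**4. Length of stay.** Assume mortality of 20% vs 10%, a usual stay of 8 days, deaths at day 5, and a 20-day stay for patients whom treatment rescues. The arms differ only in the rescued 10%, so the mean difference is 0.10 × (20 − 5) = 1.5 days longer on treatment. In 20,000 simulated trials with gamma-distributed stays and 60 per arm, treatment stay was longer in 95% and significantly longer by t test in 33%.

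The range tried was control mortality 10% to 30% halved, death day 5 to 12, and rescued stay 14 to 28 days. The mean difference runs from 0.05 × (14 − 12) = 0.1 to 0.15 × (28 − 5) = 3.45 days, and a significant result in the wrong direction occurs in 3% to 78% of trials. These percentages are for the t test; the Mann-Whitney option would give others.

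Hospital-free days to Day 28 with death scored 0, taking the mean stays as fixed, give 0.80 × 20 = 16.0 for control and 0.80 × 20 + 0.10 × 8 = 16.8 for treatment in the main case.

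**5. What a mortality comparison could deliver.** Power = Φ{[|p1−p2|√n − 1.96√(2p̄(1−p̄))] / √(p1(1−p1) + p2(1−p2))}. For 10% vs 5% and n = 60: Φ[(0.387 − 0.730)/0.371] = Φ(−0.92) = 18%.

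| Control mortality, halved | Power at 60 per arm | n per arm for 80% |
|---|---|---|
| 5% | 11% | 906 |
| 10% | 18% | 435 |
| 15% | 25% | 278 |
| 20% | 33% | 199 |
| 30% | 50% | 121 |

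For 6/60 vs 3/60 the standard error is √(0.1×0.9/60 + 0.05×0.95/60) = 0.0479, so the risk difference is 5.0 points with a 95% interval of about −4.4 to 14.4.

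**The case against.** The strongest reply is that the data are all there. A reader might infer that death is recorded only in those who die, or that mortality will never be set side by side by arm. The documents do not support either. Vital status is sought for every subject at Day 60, death is score 8 on the WHO scale, and serious adverse events are a secondary endpoint. Section 3.4 promises clinical outcomes by arm, with counts and percentages for categorical ones, and its lists are illustrative. Death counts over arm size would follow.

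Item 3 also sits under a heading covering all randomised patients, so it could be meant as raw data for a time-to-event analysis. Section 3.4 never assigns it a mean or a test.

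A reader might also infer that these endpoints must point the wrong way. They need not: steps 2 and 3 show the direction turning with the timing of deaths.

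The primary endpoint gives some protection, since "the primary efficacy end point will be the proportion of patients who achieve scores 1 or 2" counts as failures those who die without reaching that state. But it pools them with patients still in hospital, and it leaves open whether someone who reaches score 1 or 2 and dies before Day 28 stays a success.

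What stands against the reply is narrower. A descriptive count is not a specified estimate with an interval, no censoring or survival method is given, and no rule for death covers the durations, including the one that is tested.

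**Conclusion.** The gap is in the analysis, not in data collection. No between-arm estimate or survival analysis of all-cause mortality is specified, although the protocol expects the treatment to reduce it. Item 3 has values only for decedents, and raw ventilation duration and length of stay mix recovery with death, so none of the three can be read as a treatment effect.

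The practical exposure is greatest for length of stay, the only one of the three with planned tests. Under the assumed inputs, a life-saving treatment lengthens mean stay by 0.1 to 3.5 days. The size and sign of the distortion depend on mortality, timing of death and length of stay, none of which the documents state; the claim is that these endpoints can mislead, not that they will.

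These are secondary endpoints and the primary test is not affected. The change is still worth making before unblinding, because otherwise the mortality method would be chosen after the results are known.

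**What to change.** - **Mortality.** Make secondary outcome 3 all-cause mortality by Day 28 and by Day 60 in all randomised patients. Report the risk difference with 95% CI at each time, and Kaplan-Meier curves from randomisation censored at Day 60. Keep cause of death as descriptive.
- **Ventilation and length of stay.** Analyse both in all randomised patients with death given the worst value, for example ventilator-free and hospital-free days to Day 28 with death by Day 28 scored 0, compared by a rank test. A death-ranked composite would also serve. State whether death should rank below a patient still ventilated or in hospital at Day 28, since a score of 0 ties them. Raw durations can stay as description, split by survivors and deaths.

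**Cost.** Changes to the wording of Sections 3.3 and 3.4. Day 60 mortality follow-up is already planned, and death dates, ventilation days and discharge dates are needed for the present endpoints. The downside is precision: with few deaths at 60 per arm, mortality should be presented as an estimate with a wide interval, not as a powered test.
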